3 STUDY DESIGN

3.1 Description of Study Design

This is a multi-center, randomized, double-blind, placebo-controlled, dose-ranging study in 140 patients who have been diagnosed with typical Parkinson's disease within the last 3 years and are currently taking antiparkinsonian medication. Screening will be conducted within 30 days prior to the start of dosing. At baseline, eligible participants will be randomized to one of four dosage cohorts, and within each cohort will be further randomized in a 4:1 ratio to receive either active product or placebo. The assigned study product will be taken twice-daily (b.i.d.), at least 8 hours apart, for 9 months. Dosages are as follows:

- Cohort 1: 300 mg deferiprone delayed release tablets (n=28) or placebo (n=7)
- Cohort 2: 600 mg deferiprone delayed release tablets (n=28) or placebo (n=7)
- Cohort 3: 900 mg deferiprone delayed release tablets (n=28) or placebo (n=7)
- Cohort 4: 1200 mg deferiprone delayed release tablets (n=28) or placebo (n=7)

Patients will return to the site at Months 1, 2, 3, 4, 5, 6, and 9, and will receive a follow-up telephone call at Month 10. Safety will be assessed at each site visit and at the follow-up call; efficacy measures will be assessed at baseline and Months 3, 6, and 9; and sparse pharmacokinetics (PK) sampling will be done on all patients at baseline and Month 3. In addition, an optional subset of 16 patients will undergo extensive blood sampling for PK analysis at Month 1, and an optional subset of 18 patients will each provide one sample of cerebrospinal fluid (CSF) for drug level analysis at Month 3. (No selection will be done to enroll these subsets: all patients will be asked if they are willing to provide either or both of these types of samples, and they will be enrolled as they come until the total number of subjects is reached for each subset.) For safety reasons, all patients will have their absolute neutrophil count monitored weekly after the start of dosing. This procedure may be done either at either the study site or a local laboratory, or, with sponsor approval, at the patient's home by a visiting study nurse.

Any patient who withdraws before completing treatment will be requested to return within one month for an Early Termination visit, at which time the procedures normally scheduled for the Month 9 visit will be conducted.

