4.5.1 Follow-up of Patient Withdrawal Due to Pregnancy

All females of childbearing potential must have a negative serum pregnancy test at the screening visit and prior to first administration of the study drug, and must agree to use an approved method of contraception throughout the course of the trial and up to 1 month

following the last dose of study medication. If a patient does become pregnant, the investigator must do the following upon becoming aware of the pregnancy:

- Ensure that the study medication is stopped immediately
- Inform the sponsor via the pregnancy report form
- With the patient's consent, follow the pregnancy closely, and provide reports to the sponsor until delivery or other resolution

A male patient must inform the investigator if his female partner becomes pregnant during the trial or within 1 month following the last dose of study medication. As with the pregnancy of a female patient, the site must inform the sponsor and, if the partner consents, follow the pregnancy and provide the sponsor with a report on its outcome.

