- Remind patient to do the following:
 - Undergo a weekly blood draw, at either the study site or a local laboratory, or, with sponsor approval, at the patient's home by a visiting study nurse
 - o In the event of any symptoms indicative of infection such as fever, sore throat, or flu-like symptoms, immediately interrupt therapy and contact the clinic

CONFIDENTIAL

 At the next visit, bring back the completed diary card plus all medication containers, whether empty, partly used, or unopened

^{*} Must be conducted by the same qualified investigator as before, early in the morning

- In the event of a decision to withdraw from the study before completion, return to the clinic for an Early Termination Visit as soon as possible, and no later than one month following the last dose of study medication
- Schedule next study visit

Month 9 (± 5 days) – End-of-study visit/Early termination visit

Notes:

- Patients are to be instructed beforehand that on the day of this visit, they are either to not take their morning dose before coming to the site, or if they do take it, to note the time and inform the investigator of it when they arrive.
- The MDS-UPDRS and the MoCA are to be conducted early in the morning, at approximately the same time (± 1 hour) that they were done at baseline, and must be conducted by the same qualified investigator who completed them at baseline.
- If patient did not yet take the day's morning dose, administer it at this time. If patient did take the dose before arriving, record the time at which it was taken.
- Complete the MDS-UPDRS*
- Complete the MoCA*
- Collect blood samples for the following, and note the time at which they are collected:
 - Hematology and blood chemistry (including fasting glucose)
 - o Pregnancy testing for all females of childbearing potential
 - o Pharmacodynamics biomarkers (oxidative stress, inflammatory factors)
 - Mechanism of action biomarkers (ceruloplasmin levels, ceruloplasmin ferroxidase activity)
- Collect a urine sample for the following, and note the time at which it is collected:
 - Assessment of oxidative stress biomarkers
 - Urinalysis
- Complete the C-SSRS
- Review patient diary card; collect and document information on adverse events, use of concomitant medications, and treatment compliance; and file the diary card with the source documents

^{*} Must be conducted by the same qualified investigator as before, early in the morning

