7.2.1.8 Adverse Events of Special Interest

7.2.1.8.1 Neutropenia

Individuals taking deferiprone must be monitored for neutropenia, defined as a confirmed absolute neutrophil count (ANC) less than 1.5×10^9 /L. Categories of neutropenia are as follows:

Category	Black Population	All Other Races
Mild	A confirmed ANC $< 1.0 \times 10^9/L$ but $\ge 0.65 \times 10^9/L$	A confirmed ANC $< 1.5 \times 10^9$ /L but $\ge 1.0 \times 10^9$ /L
Moderate	A confirmed ANC $< 0.65 \times 10^9/L$ but $\ge 0.5 \times 10^9/L$	A confirmed ANC $< 1.0 \times 10^9$ /L but $\ge 0.5 \times 10^9$ /L
Severe/agranulocytosis	A confirmed ANC $< 0.5 \times 10^9 / L$	

For a case of neutropenia to be confirmed, there must be 2 consecutive counts, a maximum of 3 days apart, that are both less than the specified value. If the 2 counts are not in the same severity category, a third count will be required to determine the severity. If a patient has just a single ANC value less than $1.5 \times 10^9/L$ ($< 1.0 \times 10^9/L$ for a black patient), this is to be documented in the CRF as an AE of "decreased ANC", but is not to be defined as neutropenia. The investigator is to use judgment as to whether the decrease is clinically significant.

In addition to having ANC monitored, patients will be advised to immediately report any symptoms indicative of infection such as fever (≥ 38.5 °C), sore throat, and flu-like symptoms at any time during treatment or during the first week following treatment. They will be

provided with an emergency services card with contact information, and advised to carry it with them at all times.

Depending of the severity of neutropenia, patients will either remain in or be withdrawn from the study. The management of different severities of neutropenia is described below.

Mild and moderate neutropenia:

A patient who develops either mild or moderate neutropenia is to interrupt treatment as soon as the neutropenia is confirmed, and ANC is to be monitored every 2 days until resolution.

The patient should re-initiate treatment once the event is resolved, defined as 2 consecutive ANC $\geq 1.5 \times 10^9$ /L (ANC $\geq 1.0 \times 10^9$ /L for a black patient). If ANC is still $< 1.5 \times 10^9$ /L after 14 days, the investigator is to do the following:

- Withdraw patient from the study and monitor him/her until resolution of the event
- Advise patient regarding protective isolation

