- Examine patient the same day (if possible), including drug history and physical examination
- Notify ApoPharma Inc. using the SAE form

Severe neutropenia/agranulocytosis:

A patient in whom a single ANC measurement $< 0.5 \times 10^9 / L$ is detected is to immediately stop treatment, without waiting for confirmation of the count, and a second measurement is to be done the following day. If the second ANC is still $< 0.5 \times 10^9 / L$, the patient is to be permanently withdrawn from the study, and ANC is to be monitored daily until resolution. The following procedures should be done by the investigator or the treating physician, as appropriate:

- Provide protective isolation; if clinically indicated, admit patient to hospital and obtain vital signs every 4 hours
- Examine the patient the same day, if possible, including drug history and physical examination
- With the patient's consent, collect a blood sample to attempt to identify genetic or other biomarkers related to agranulocytosis
- Notify ApoPharma Inc. using the SAE form.

The following additional measures describe a suggested medical management and monitoring:

- If possible, consider obtaining bone marrow aspirate for:
 - Histology
 - Progenitor culture
 - o Frozen storage (1 mL sample)
- If possible, consider obtaining bone marrow biopsy (minimum length 3 mm)
- Perform septic work-up including chest X-ray, blood, urine, and throat cultures
- Obtain q4h temperatures from patient (monitored by family at home if patient is not in the hospital)
- If warranted, administer granulocyte stimulating factors, such as G-CSF 10 μ g/kg, on an in-patient basis if possible, beginning the same day that the ANC is confirmed as $< 0.5 \times 10^9$ /L; administer daily until ANC is $> 1.5 \times 10^9$ /L on 2 consecutive days
- If ANC < 0.5 x 10⁹/L for 7 days, repeat bone marrow biopsy and aspirate weekly during the period of agranulocytosis, if warranted

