7.2.4 Procedures in Case of Pregnancy

If a patient becomes pregnant during the course of the study, she will be immediately withdrawn. The pregnancy is to be immediately reported to the sponsor, and information about the pregnancy is to be recorded on the appropriate form and in the patient's eCRF. The patient will be followed to determine the outcome, and any premature termination of the pregnancy will be reported. Upon delivery, the child will be examined for any adverse symptoms or congenital anomalies. Follow-up information on the status of the mother and child will be forwarded to the sponsor no later than 8 weeks following the delivery.

If the partner of a male patient becomes pregnant during the course of the study, or if the fetus may have been exposed to the patient's study products either through maternal exposure or through transmission via semen following paternal exposure, the pregnancy must be reported to the sponsor, and information about the pregnancy must be recorded on the appropriate form and in the patient's eCRF. If the partner provides consent for follow-up of the pregnancy, she will be followed until the delivery of the child, and information on the delivery status of the mother and child will be forwarded to the sponsor no later than 8 weeks following the delivery date.

Any SAE occurring as a result of a post-study pregnancy that the investigator believes may have been caused by the study product or by a protocol procedure will be reported to the sponsor as described in Section 7.2.1.6.

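### The shared Month 9/Early Termination visit list tells the site to give that day's morning dose without limiting this to patients still on study drug; read literally, it conflicts with the protocol's stop rules.

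*Protocol*

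**What the plan says.** The last visit list in section 5.1 is headed for two visits at once: "End-of-study visit/Early termination visit". Its first action item is "If patient did not yet take the day's morning dose, administer it at this time", followed by an instruction to record the time if the patient took the dose before arriving. A note above the list tells patients beforehand either to hold the morning dose or to take it and report the time.

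Section 3.1 asks anyone who withdraws before completing treatment to return within one month for an Early Termination visit, "at which time the procedures normally scheduled for the Month 9 visit will be conducted". The synopsis says the same, and Table 5.1 puts Month 9 and Early Termination in one column. None of these places makes an exception for dosing.

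The stop rules are elsewhere:

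- **Severe neutropenia/agranulocytosis (7.2.1.8.1).** A patient with a single ANC below 0.5 × 10⁹/L "is to immediately stop treatment, without waiting for confirmation of the count". If the next day's count is still below that level, withdrawal is permanent.
- **Mild or moderate neutropenia (7.2.1.8.1).** The patient "is to interrupt treatment as soon as the neutropenia is confirmed" and restarts only after resolution. If the count is still low after 14 days, the instruction is "Withdraw patient from the study and monitor him/her until resolution of the event".
- **Pregnancy (4.5.1 and 7.2.4).** The investigator must "Ensure that the study medication is stopped immediately". Section 7.2.4 adds: "If a patient becomes pregnant during the course of the study, she will be immediately withdrawn".

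**The concern.** A patient taken off study drug has, by definition, not taken a dose that morning. The dosing line's only condition is therefore met by exactly the patients for whom the drug must stay stopped. A coordinator working down the list for someone withdrawn for agranulocytosis or pregnancy would find an instruction to dose and, in that list, nothing against it.

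The stakes are clinical. Section 1.4 describes agranulocytosis as the most serious adverse event seen with deferiprone in systemic iron overload, says that it usually resolves once the drug is stopped, and notes post-marketing deaths. A dose at Early Termination would also move the last-dose date from which the 30-day SAE window runs (sections 7.2.1.2 and 7.2.1.6).

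**Working it through.** The plan gives no figure to reproduce on this point. The check is a comparison of texts.

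**Step 1: who attends.** Sections 3.1 and 4.5 describe the Early Termination visit as the return of a patient who has withdrawn or been withdrawn. That group includes patients withdrawn under the three stop rules.

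**Step 2: what the line requires.** It asks only whether today's dose was taken. For a patient already off drug the answer is no, so the literal instruction is to dose.

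**Step 3: compare with each stop rule.**

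| Reason for withdrawal | What the rule requires | Literal effect of the visit line |
|---|---|---|
| Agranulocytosis | Stop at once; permanent withdrawal if confirmed | One further dose |
| Neutropenia unresolved after 14 days | Drug already interrupted; withdraw | One further dose |
| Pregnancy | Stop at once; withdraw | One further dose |

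**Step 4: look for an exemption.** None appears in sections 3.1, 4.5, 4.5.1, 5.1, 7.2.1.8.1 or 7.2.4, or in Table 5.1. Other items in the same list are qualified or adapted. Contraceptive counseling is to be done only where applicable. The pregnancy test omits the Month 6 condition that a negative result is needed to continue. The dosing line is almost the same as at Month 6 and was not adapted. At Month 6 the safety bloods are listed before the dose; in this list they come after it.

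**Step 5: what can be sized.** The documents give no basis for a re-dosing rate. The nearest figure is how many patients might reach the agranulocytosis rule. Inputs are 112 active patients (section 5.2) and the pooled rate of about 2% (section 1.4). That rate comes from patients with systemic iron overload and has no stated exposure time, so carrying it over is an assumption. The two lower rates are assumed as well.

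| Rate | Expected patients, 112 × rate | Chance of at least one, 1 − (1 − rate)¹¹² |
|---|---|---|
| 2% | 112 × 0.02 = 2.24 | 1 − 0.98¹¹² = 0.896 |
| 1% | 112 × 0.01 = 1.12 | 1 − 0.99¹¹² = 0.676 |
| 0.5% | 112 × 0.005 = 0.56 | 1 − 0.995¹¹² = 0.430 |

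These figures count patients who could meet the conflicting texts by that one route. They do not measure re-dosing and carry no weight in judging how likely it is. No upper limit on time off drug can be fixed either. The one-month limit counted from the last dose (section 5.1) addresses patients who decide to withdraw, and section 4.5 counts from withdrawal and says only that the patient should return.

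**The case against.** The best answer is that the texts can be followed together. A morning dose not yet taken presupposes a dose that is due, and a patient whose drug has been stopped has none due. The pre-visit note also assumes someone still taking tablets. Section 5.1 times Early Termination from the last dose for patients who decide to leave, which places that dose before the visit. Section 4.5 has withdrawn patients hand back their product. The stop rules are specific and safety-driven, while the visit list is generic. Months 1 and 3 tell the site to give the morning dose with no condition at all, although a continuing patient may be under a mandatory interruption for infection or neutropenia. Visit lists therefore seem to assume that treatment has not been stopped.

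Much of this stands. It makes actual re-dosing unlikely. A reader might infer that the protocol means withdrawn patients to be re-dosed, or that about two patients would be. The documents support neither inference: the wording allows the milder reading, and the figure of about two counts patients reaching a stop rule.

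The objection does not remove the point. The protocol never states the milder reading or says that the stop rules take precedence. Months 1, 3 and 6 are for continuing patients, whereas this list expressly serves patients who have withdrawn, so the assumption that treatment continues fails for the Early Termination half of its heading. Return of product gives limited protection, because the same list collects containers after the dosing line.

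**Conclusion.** Wrong as written, in a limited sense. One instruction in section 5.1, read literally at an Early Termination visit, conflicts with the stop rules for agranulocytosis, unresolved neutropenia and pregnancy. It is a low-probability drafting error with a patient-safety aspect. The possible harm is a single dose of 300 to 1200 mg in an active arm; its probability cannot be derived from the document. The definition of the primary endpoint and its analysis are untouched. The conclusion rests on the literal wording and on the absence of any stated exemption. It assumes nothing about the sponsor's intent or about how sites behave. The point is worth correcting because the patients concerned include those whose drug was stopped for safety and the correction costs almost nothing.

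**What to change.** In section 5.1, attach one restriction to both the dosing line and the pre-visit morning-dose note in the Month 9/Early Termination list: *Month 9 visit only, for patients still taking study drug; do not administer study drug at an Early Termination visit.* A single restriction is enough, and the stop rules need no change. The cost is one wording amendment and a memo to sites, with no added visits, patients or data items.

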5.2 Method of Assignment to Treatment

At baseline, 140 eligible participants will be randomized to one of four dosage cohorts (n=35 each), and within each cohort will be further randomized in a 4:1 ratio to receive either active product (n=28) or placebo (n=7). Thus, a total of 112 patients will receive one of the four dosages of deferiprone, and a total of 28 will receive placebo.

The sponsor will generate the randomization codes according to the study design. Once generated, the randomization codes will be final and will not be modifiable. An IVRS/IWRS will be used to perform the randomization in this study.

5.3 Blinding Procedures

The placebo tablets will have the same appearance as the deferiprone tablets. Within each cohort, all participants will take the same number of tablets at each dose: 1 half-tablet in Cohort 1; 1 tablet in Cohort 2; 1.5 tablets in Cohort 3; and 2 tablets in Cohort 4.

Sites will be provided with code-breaking instructions. In the event of an emergency, the randomization code may be broken only if knowledge of the respective treatment is necessary for adequate treatment of the emergency. The sponsor must be contacted within 24 hours in case of unblinding. Randomization information will be held by designated individual(s). The date and reason for breaking the blind must be documented.

5.4 Allocation of Patient Numbers

After provision of informed consent, each patient will be assigned a unique ID number and will be identified in all study data by this number. The ID number will consist of 6 digits, where the first digit represents the country code, the next 2 digits represent the site code (01 for site #1, 02 for site #2, etc.), and the next 3 digits (separated from the first 3 by a hyphen) are assigned sequentially for each individual screened at that site. For example, if site #1 from the country designated as "1" screens 8 patients, the ID numbers will be 101-001 through 101-008. The assigned ID numbers of patients who are screening failures or who withdraw from the study will not be reused.

5.5 Treatment Compliance

Compliance will be determined as follows: 1) the patient will use the daily diary card to record the number of tablets taken, and 2) at each visit, the investigator or delegate will inspect the medication containers whether empty, partly used, or unopened, and will check the number of tablets remaining. Compliance will be calculated by the number of tablets taken divided by the number of tablets prescribed as per the dosing frequency and length of treatment. Any discrepancies must be discussed with the patient and documented in the source documents. Reasons for non-compliance with the treatment will be recorded in the source document and in the eCRFs. The investigator should discuss treatment compliance with the patient at each visit.

If the number of returned tablets is less than it should be, but the patient reports having taken the correct amount of medication, the site will report compliance as 100% in the eCRF, and will provide the reason for the apparent over-compliance (e.g., tablets were accidentally spoiled and could not be ingested), along with the actual percentage. Both undercompliance < 80% and over-compliance >120% will be reported as a protocol deviation, unless under-compliance is due to treatment interruption because of infection or neutropenia or other extenuating circumstances (see Section 7.2.1.8).

6 STUDY TREATMENTS

Patients will receive either deferiprone delayed release tablets or placebo tablets.

6.1 Investigational Product

Deferiprone delayed release tablets are manufactured by Apotex Inc., and will be supplied to the clinical sites by ApoPharma Inc. The tablets are biconvex, capsule-shaped, white to offwhite in color, enteric-coated, engraved with "APO 400" on one side, and scored on both sides. Each tablet contains 600 mg of deferiprone. Non-medicinal ingredients are hypromellose acetate succinate, magnesium oxide, magnesium stearate, colloidal silicon dioxide, triethyl citrate, sucrose, talc 500 mesh, methacrylic acid copolymer dispersion, and titanium dioxide.

